**Objective set 2- Veterans in care with no evidence of HIV infection who are not on PrEP but could benefit from PrEP**

- 2.1- Describe the characteristics of Veterans in care who are not on PrEP but could benefit from PrEP
- 2.2- Estimate HIV testing and diagnoses rates, as well as rates of STI screening/testing rates, STI diagnoses among Veterans in care who are not on PrEP but could benefit from PrEP, over a 12-month period of follow-up

**Objective set 3- Veterans on care with no evidence of HIV infection who initiate PrEP (oral or CAB LA injectable) during the study period**

- 3.1- Describe the population of Veterans in care who initiated oral PrEP or CAB LA injectable PrEP, including their demographic, clinical and sexual behavioral characteristics, the year of PrEP initiation and the duration of follow-up
- 3.2- Describe the proportions of Veterans on care initiating CAB LA PrEP who used oral lead in (OLI) and proportion of those with direct to injection (DTI).
- 3.3- Describe adherence to oral and CAB LA injectable PrEP
- a) Oral PrEP use only: number days oral PrEP supplied divided by number of days in observational period
  - b) CAB LA injectable PrEP
    - Number of days covered by CAB LA PrEP divided by the number of days in the observation period
    - Timing and completion of initiation injections
    - Among complete initiators with at least one maintenance injection, timing of maintenance injections: all on time, any late injection (short delay not requiring reinitiation, long delay requiring reinitiation)
    - Baseline characteristics of users with all injections on time versus users with any late maintenance injection
- 3.4- Describe patterns of PrEP use
- a) Oral PrEP:
    - Discontinuation: any discontinuation, resumption of oral PrEP
    - Duration of oral PrEP use for the first period of use
  - b) CAB LA injectable PrEP
    - Discontinuation: any discontinuation, resumption of long-acting injections (with CAB LA injectable or LEN LA injectable) or oral PrEP after discontinuation
    - Oral bridging between discontinuation of CAB LA injections and resumption of CAB LA injections
    - Duration of CAB LA PrEP use in months

- first period of use
  - cumulative use throughout the study period in case of discontinuation followed by resumption of CAB LA PrEP injection(s)
  - Baseline characteristics of users discontinuing CAB LA PrEP versus users who did not discontinue

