## **7. RESEARCH METHODS**

### **7.1. Study Design**

This is a cohort study using data from the Veterans Affairs National Sample, which is composed of Veterans who receive healthcare services through the Veterans Health Administration (VHA). This national sample is representative of the Veteran population, capturing a wide range of demographic, clinical, and social characteristics.

Data will be extracted from VHA's Corporate Data Warehouse (CDW), a comprehensive, regularly updated repository of information from VHA's electronic health records and administrative files. It includes patient-level data such as demographics, clinical encounters (diagnoses, interventions), laboratory and imaging results, medication details, health services utilization, and long-term health outcomes.

The study period will range from January 1, 2021, to December 31, 2025. Initiation of PrEP regimen will be assessed during the period January 1, 2021 to June 30, 2025, to allow for at least 6 months of observation following PrEP initiation.

The study will include different cohorts, as described in Table 2.

Veterans who are not on PrEP but could benefit from PrEP will be identified based on risk factors for HIV acquisition or factors linked to behaviors increasing the risk of HIV acquisition which are generally documented in Veterans health records. These risk factors include: tested for or diagnosed with a bacterial STI in the past 12 months (gonorrhea, syphilis, chlamydia) (US CDC, 2024), tested for HIV in the past 12 months, ever had alcohol use disorder (Williams, 2016), ever used illicit non-injection drugs (HIV.gov, 2024), ever used injectable drugs (CDC, 2024), Black women (CDC, 2024; Reaves, 2025), men who have sex with men (CDC, 2022; Mayer, 2021), individuals aged 18-24 years (HIV.gov, 2025 b), any history of PrEP use (Hojilla, 2021; Krakower, 2019).

---

 The US CDC recommends PrEP for people with a bacterial STI diagnosis in the past 6 months. This has been extended to testing for a bacterial STI in the past 12 months for this protocol.

**Table 2:** Description of study cohorts

Objectives	Criteria	
Objective 1a - Among all Veterans without evidence of HIV infection	Population/exposure	No evidence of HIV diagnosis at beginning of each calendar year of the study period under analysis
	Index date	N/A
	Censoring criteria	N/A
	Endpoint	HIV diagnosis

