Objective 1b - Among Veterans with a new HIV diagnosis during the study period	Index date	Date of HIV diagnosis
	Censoring criteria	NA
	Endpoint	PrEP use (never, use within 12 months before diagnosis, use >12 months before diagnosis)
Objective set 2 – among Veterans without evidence of HIV infection who are not on PrEP but could benefits from PrEP	Population/exposure	At least one of the following criteria: tested for or diagnosed with a bacterial STI in the past 12 months (gonorrhea, syphilis, chlamydia), tested for HIV in the past 12 months, ever had alcohol use disorder, ever used illicit non-injection drugs, ever used injectable drugs, Black women, men who have sex with men, individuals aged 18-24 years, any history of PrEP use
	Index date	First visit during the study period with criteria indicating the individual could benefit from PrEP
	Censoring criteria	Death, loss to follow-up, end of the study period, 12 months after index date, PrEP initiation, whatever comes first
	Endpoints	HIV testing, HIV diagnosis, Screening/testing for other STIs, STI diagnoses
Objective set 3 – among Veterans with a PrEP prescription	Exposure groups	Oral PrEP, CAB LA PrEP
	Index date	Start of first PrEP regimen during the study period (dispensing date for oral PrEP, injection date for CAB LA)
	Censoring criteria for calculation of proportion of days covered	Death, loss to follow-up (12 months after last clinical contact), study end, 12 months after index date whatever comes first
	Endpoints	Adherence to PrEP schedule, discontinuation and resumption of PrEP, STI screening/testing, STI diagnosis, STI treatment prescription, HIV testing and diagnosis

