## 7.2. Study Population and Setting

### 7.2.1. Inclusion criteria

- **Veterans in care without evidence of HIV infection (Obj. 1.1)- individuals will be included if they meet all of the following criteria:**

- At least one VHA health encounter in the calendar year
- $\geq 18$  years of age
- No evidence of HIV infection at the beginning of the calendar year under analysis

- **Veterans in care with a new HIV diagnosis (Obj. 1.2):**

- Incident HIV diagnosis (refer to definition in section 7.3.3)

- **Veterans in care without evidence of HIV infection who are not on PrEP but who could benefit from PrEP (Objective set 2)- individuals meeting all of the following criteria:**

- At least one VHA health encounter during the study period
- $\geq 18$  years of age
- Any of the following criteria indicating that the individual has a risk factor for HIV acquisition or a factor linked to behaviors increasing the risk of HIV acquisition and may benefit from PrEP:
  - tested for or diagnosed with a bacterial STI in the past 12 months (gonorrhea, syphilis, chlamydia),
  - tested for HIV in the past 12 months,
  - ever had alcohol use disorder,
  - ever used illicit non-injection drugs,
  - ever used injectable drugs,
  - Black women,
  - men who have sex with men,
  - individuals aged 18-24 years,
  - any history of PrEP use
- No evidence of HIV infection at the first health encounter with a criteria for PrEP

- **Veterans in care using oral PrEP only (objective set 3)**

- At least one VHA health encounter during the study period
- $\geq 18$  years of age
- Received at least one oral PrEP prescription (TDF/FTC, TAF/FTC) between January 1 2021 and 31 December 2024
- No evidence of HIV infection at the time of the first oral PrEP prescription in the study period
- Have not received a CAB LA PrEP injection between January 1, 2021, and June 30, 2025

- **Veterans in care using CAB LA for PrEP (objective set 3)**

- At least one VHA health encounter during the study period
- $\geq 18$  years of age
- Received at least one CAB LA PrEP injection between January 1, 2021 and June 30, 2025

- No evidence of HIV infection at the time of the first CAB LA PrEP injection in the study period

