## **7.9. Limitations of the research methods**

CAB LA PrEP injections are directly observed in clinical settings; thus, injection records in the EHR provide certainty that PrEP was received and the exact timing of injections. In contrast, oral PrEP use and timing cannot be ascertained with the same level of precision. Oral PrEP dispensing is a proxy for PrEP use. The date of oral PrEP initiation is defined as the first PrEP dispensing date; subsequent PrEP dispensing events are considered renewals.

The identification of incident HIV diagnosis relies on HIV testing being conducted. Therefore, information on incident HIV diagnosis and exact timing may be subject to measurement error.

In addition, detailed behavioral and personal information indicating that an individual could benefit from PrEP is not systematically recorded in the EHR. Thus, Veterans who are not on PrEP but could benefit from PrEP will be identified based on risk factors for HIV acquisition or factors linked to behaviors increasing the risk of HIV acquisition which are generally documented in Veterans health records. This approach may result in identifying a broader group of individuals than if individual detailed behavioral information was available.

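### The oral PrEP cohort is described as initiators, but no PrEP-free look-back is required, so Veterans on oral PrEP before 2021 can be indexed at a refill

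*Protocol*

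**What the plan says.** Section 6 names the population of Objective set 3 as "Veterans on care with no evidence of HIV infection who initiate PrEP (oral or CAB LA injectable) during the study period", and Objective 3.1 is to "Describe the population of Veterans in care who initiated oral PrEP or CAB LA injectable PrEP". Section 7.1 states that "Initiation of PrEP regimen will be assessed during the period January 1, 2021 to June 30, 2025". These passages are about starting PrEP.

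The oral criteria in Section 7.2.1 are about having a prescription. Apart from age and a VHA encounter, there are three. The first is "Received at least one oral PrEP prescription (TDF/FTC, TAF/FTC) between January 1 2021 and 31 December 2024". The second ties HIV-negative status to a prescription inside the window, with the words "No evidence of HIV infection at the time of the first oral PrEP prescription in the study period". The third rules out anyone injected with CAB LA from the start of 2021 to the middle of 2025.

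The Objective set 3 index date in Table 2 is "Start of first PrEP regimen during the study period (dispensing date for oral PrEP, injection date for CAB LA". Section 7.9 adds: "The date of oral PrEP initiation is defined as the first PrEP dispensing date; subsequent PrEP dispensing events are considered renewals". It does not say whether the first dispensing is the first ever or the first in the window.

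Prior PrEP use is listed among the baseline characteristics in Section 7.3.2. Nothing in Section 7.7 uses it to exclude or stratify.

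**The concern.** Section 5 says that oral PrEP was approved in July 2012 and that VHA counted 361 Veterans prescribed PrEP in 2014 and 6,050 in 2022. So there were Veterans on oral PrEP when the window opened on 1 January 2021. Under the inclusion criteria they qualify at their first prescription on or after that date.

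Most oral outcomes in Objective set 3 count time from initiation. If the index is a refill, that time zero is arbitrary, and the results describe a mixture of new starters and Veterans who had already stayed on PrEP past the early period. A reader would take tables titled as initiators to show what happens after starting oral PrEP, and for part of the cohort they would not.

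**Working it through.** **1. Does any criterion keep a continuing user out?** Take a Veteran on oral PrEP since 2018 who refills in January 2021, is HIV-negative and has no CAB LA injection.
- Prescription in the window: met.
- No evidence of HIV at the first prescription in the study period: met. This wording itself allows for earlier prescriptions.
- No CAB LA injection: met.

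The Veteran is admitted. On the Section 7.2.1 anchor the entry point is the January 2021 prescription. If Section 7.9 is read as first dispensing ever, the January 2021 dispensing is a renewal, and an admitted Veteran has no start inside the window. The passages conflict on either reading, and neither keeps the Veteran out.

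**2. What happens to each outcome for that Veteran?**

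| Outcome | Where | Effect |
|---|---|---|
| Duration of first period of oral use | 7.3.3, Obj. 3.4 | Left-truncated: time before 2021 is lost |
| 12-month coverage; discontinuation | 7.3.3, Obj. 3.3 and 3.4 | Later PrEP time pooled with the first months of true starters |
| Year of initiation | 6, Obj. 3.1 | Wrong year |
| STI testing and diagnosis in the six months before initiation | 6, Obj. 3.5b | Window is on-PrEP time |
| HIV test at or within 7 days before start | 7.3.3, Obj. 3.5 | Tied to a refill, on treated time |

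**3. The plan's precision figures.** Section 7.5 uses p ± 1.96·√(p(1−p)/N). For N = 15,477 and p = 0.5, the width is 2 × 1.96 × √(0.25/15,477) = 0.0158, which matches the printed 0.02. All 18 widths in Table 4 reproduce. The base is described there as users, counted to 30 June 2025, whereas oral eligibility ends on 31 December 2024.

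**4. Illustrative number of continuing users.** The documents give no count for 2020. Interpolating between 2014 and 2022:
- linear: 361 + (6,050 − 361) × 6/8 = 4,628
- geometric: 361 × (6,050/361)^(6/8) = 2,990

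Assume that 40% to 80% of them had a further dispensing inside the window:
- low: 2,990 × 0.4 = 1,196, and 1,196/15,477 = 7.7%
- high: 4,628 × 0.8 = 3,702, and 3,702/15,477 = 23.9%

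**5. Precision after restricting to initiators** (width at p = 0.5):
- N = 15,477 − 1,196 = 14,281: 0.0164
- N = 15,477 − 3,702 = 11,775: 0.0181

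**6. Sensitivity of a pooled proportion.** If continuing users are a share s of the cohort and their proportion differs from that of starters by d, the pooled figure moves by s × d. With d assumed to be 10 to 30 points, the shift runs from 0.08 × 10 = 0.8 points to 0.24 × 30 = 7.2 points. The current half-width at p = 0.5 is about 0.8 points. The documents give no value or sign for d; this shows only that the mixture can matter more than sampling error.

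**The case against.** The best case for the plan is that its wording points to a true start. Table 2 speaks of the start of a first regimen, Section 7.1 of initiation, and Section 7.9 calls later dispensings renewals. This stands as far as it goes: the text is ambiguous, and it cannot be said that every pre-2021 user will be counted as a new start. But no criterion enforces the initiator reading, and the Section 7.2.1 anchor works against it.

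Second, prior PrEP use is collected at index, so a split into new and continuing users is possible, and an analysis plan not seen here might specify one. That is a partial mitigation. Eligibility and index date are fixed in the protocol, and they are where the conflict lies.

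Third, Table 2 also describes the set as Veterans with a PrEP prescription, and Section 7.5 aims at usage in clinical practice. Continuing users are a legitimate part of that picture, which argues for showing them separately rather than dropping them.

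A reader might also infer several stronger things that the documents do not support:
- *Oral persistence is overstated relative to CAB LA.* No oral-versus-CAB LA test or effect estimate is planned. For duration the direction is mixed, because truncation removes time from continuing users. No figure fixes the size or sign for adherence.
- *Only the oral group is affected.* CAB LA was approved in December 2021, so a first injection is normally a true CAB LA start, but not necessarily a first use of PrEP. The VHA access criteria in Section 5 include intolerance of oral PrEP and difficulty adhering to it, and the Objective 3.6 timelines list oral prescriptions before CAB LA. The pre-initiation window can be on-PrEP time there too.
- *The start-of-PrEP HIV test will be missing for continuing users.* Section 5 describes visits every three months for repeat tests and refills, so a test may well coincide with the index refill. What it would not be is a test before starting.

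**Conclusion.** The point holds as a conflict of definitions with consequences for the results. Objective set 3 is framed as initiators, the oral inclusion rule admits users, and nothing in the protocol separates the two in the analysis. Duration, 12-month coverage, discontinuation, year of initiation, the pre-initiation STI window and the start-of-PrEP HIV test are all affected for continuing users. The problem with the pre-initiation window extends to CAB LA users with prior oral PrEP.

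The size is uncertain. The 8-24% share rests on interpolation between two annual counts, an assumed carry-over of 40-80%, and a base of 15,477 that may not be the eligible oral cohort because the end dates differ. It should be read as an illustration, not an estimate. That the inclusion rule admits continuing users does not depend on it.

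**What to change.** Before the cohort is built:

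1. In Section 7.2.1, define an oral initiator by an explicit look-back with no oral PrEP dispensing before index, for example 365 days, with another length as a sensitivity analysis. The documents do not dictate the length; what matters is that one is fixed. Section 7.4 describes a data source that reaches back to 2000.
2. Align Table 2 and Section 7.9 with that definition, stating whether the first dispensing means first ever, first in the window, or first after the look-back.
3. Report adherence, discontinuation, duration and Objective 3.5 results for initiators, with continuing users shown separately.
4. Show CAB LA results by prior oral PrEP use.
5. Reconcile the end of the oral window (31 December 2024 in Section 7.2.1, 30 June 2025 in Sections 7.1 and 7.5), and restate the oral N and Table 4 in Section 7.5.

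The cost is one added criterion, one rerun of the feasibility count and a somewhat smaller oral cohort, about 11,800 to 14,300 on the assumptions above. The widest oral interval would go from 0.016 to at most about 0.018.

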**a) Oral PrEP coverage in the 12 months following initiation**

PrEP dispensing is considered as a proxy for PrEP use. The number of dispensing events will be described.

The number of pills dispensed/days covered per dispensing event will be calculated.

Proportion of days of access to oral PrEP in the 12 months following index PrEP initiation

Follow-up (FU) will be censored at first of:

- 12 months after index date
- Loss to follow-up
- Death
- Study end

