**b) Adherence to CAB LA PrEP schedule**

- Proportion of days covered by CAB LA PrEP in the 12 months following initiation: number of days covered by CAB LA PrEP divided by the number of days in the observation period

Follow-up will be censored at first of:

- a) 12 months after index date
- b) Loss to follow-up
- c) Death
- d) Study end

Coverage by LA PrEP will be determined based on the duration of days covered by the medication, according to the label.

- 1st injection: coverage = 37 days (30 days of coverage + 7-day injection window)
- Subsequent injections: coverage = 67 days (60 days of coverage + 7-day injection window)

Each calendar day will only be counted once, even if there is an overlap between coverage from the prior injection and date of the next injection.

- **Complete versus incomplete initiation:**

- Among all Veterans with  $\geq 1$  CAB LA injection:

→ Complete initiation (2nd injection received within 67 days following the 1st injection)

- 2nd initiation injection on time: 2nd injection between 23 and 37 days following the first injection
- 2nd initiation injection late: 2nd injection between 38 and 67 days following the first injection

→ Incomplete initiation: >67 days without injection following the first injection

- Among incomplete initiators

Any additional injection(s) >67 days after the 1st injection (Yes/no)

If yes:

- o Timing of the 1st additional injection after the last injection of the “incomplete initiation” (interval in days, number with interval of 68-97 days and interval >97 days)
- o Complete versus incomplete reinitiation
- o Interval between the first two reinitiation injections ( $\leq 37$ ; 38-67, 68-97, 98-127;  $\geq 128$  days apart)

• **Timing of CAB LA PrEP maintenance injections:** among complete initiators with at least one maintenance injection

Determined based on the time between initiation injections (Table 3)

- Total number of maintenance injections per individual
- All on time
- Any late maintenance injection (short delays not requiring reinitiation, long delays requiring reinitiation): number of short and long delays, number of individuals with 1, 2, 3 or more short delays, number of individuals with 1, 2, 3 or more long delays, median duration of short and of long delays

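### The 12-month coverage figures count days on another PrEP as uncovered, and the oral and CAB LA cohorts do not handle switching alike

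*Protocol*

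**What the plan says.** Table 2 (Section 7.1) gives the censoring events for the coverage calculation: "Death, loss to follow-up (12 months after last clinical contact), study end, 12 months after index date whatever comes first". Section 7.3.3, Adherence, parts a and b, lists the same four events for oral and for CAB LA users.

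The measures are specific to the modality. For CAB LA it is the "number of days covered by CAB LA PrEP divided by the number of days in the observation period", with fixed credits per injection: for the first "injection: coverage = 37 days (30 days of coverage + 7-day injection window"), and after that "Subsequent injections: coverage = 67 days (60 days of coverage + 7-day injection window"). For oral users it is the "Proportion of days of access to oral PrEP in the 12 months following index PrEP initiation". Both belong to Objective 3.3, which is headed adherence, and Section 7.7.1.1 describes the two percentages in one sentence over the same 12 months.

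Changes of PrEP are expected. Objective 3.4 b (Section 6) covers "resumption of long-acting injections (with CAB LA injectable or LEN LA injectable) or oral PrEP after discontinuation", and also oral bridging. Neither is linked to the coverage measure.

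Section 7.2.1 admits oral users who "Received at least one oral PrEP prescription (TDF/FTC, TAF/FTC) between January 1 2021 and 31 December 2024", provided they "Have not received a CAB LA PrEP injection between January 1, 2021, and June 30, 2025". The CAB LA cohort has no matching exclusion for later use of other PrEP.

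**The concern.** A coverage figure presented as adherence should not mix three different things: injections given late, PrEP stopped altogether, and PrEP continued in another form. As fixed here, the second and third look the same. A Veteran who goes from CAB LA straight to daily tablets gets the same score as one who stops all PrEP on that day.

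Persistence already has its own objective. Objective 3.4 reports discontinuation, months on regimen, and CAB LA status at 12 and 24 months. The protocol does not say that the Objective 3.3 figure is also partly a persistence figure. Table 2 does censor at PrEP initiation for Objective set 2 (the list in Section 7.3.3 for that set does not), so a change of PrEP status was considered a censoring event for another cohort but not for this measure.

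The exclusion in the oral cohort adds a second problem. It uses information from after the index date to remove oral users who later received CAB LA. Section 5 names difficulty with daily oral adherence as one qualifying route to CAB LA within VHA, so those removed may not be typical of oral users. Readers will set the two percentages side by side even though no test compares them.

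**Working it through.** **Planning figure.** The protocol has none for coverage. Its precision table (Table 4) is for binary proportions: for p = 0.8 and N = 748, 1.96 × √(0.8 × 0.2 / 748) = 0.029, giving 0.771 to 0.829. This reproduces the stated 77-83%. It is not an input here, and its widths are no benchmark for mean coverage.

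**Inputs from the protocol.** 37 days credited for the first injection and 67 for each later one, each calendar day counted once (7.3.3 b); a 12-month window, taken as 365 days.

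**Assumptions.** Injections on days 0, 30, 90, 150 and so on; a switch to other PrEP on the next due day. The protocol gives no number or timing of switches.

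**One person.** Score = distinct days covered by CAB LA / observation days. For a switch at day 150, the injections on days 0, 30 and 90 cover days 0-36, 30-96 and 90-156, together 157 distinct days. As written: 157/365 = 43.0%. Censored at the switch: 150/150 = 100%.

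| Switch day | As written | Censored at switch |
|---|---|---|
| 90 | 97/365 = 26.6% | 100% |
| 150 | 157/365 = 43.0% | 100% |
| 210 | 217/365 = 59.5% | 100% |
| 270 | 277/365 = 75.9% | 100% |
| 330 | 337/365 = 92.3% | 100% |

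**Oral bridging.** Suppose the user injected on days 0, 30 and 90 bridges with oral PrEP and resumes injections on days 300 and 330. CAB LA covers 157 days plus days 300-364 (65 days): 222/365 = 60.8%. The other 143 days count as uncovered whatever was dispensed. Censoring at the first oral dispensing would instead discard the resumed injections.

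**Cohort mean.** If a share s switches at day 150 and all others are fully covered, the mean falls by s × (1 − 0.430):

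- s = 5%: 0.05 × 0.570 = 2.8 points (mean 97.2%)
- s = 10%: 5.7 points (94.3%)
- s = 20%: 11.4 points (88.6%)

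**Quartiles.** Section 7.7.1.1 reports median and interquartile range. If switchers are the lowest scorers, the reported median is the (0.50 − s)/(1 − s) quantile of the others: 0.45/0.95 = 47th percentile at 5%, 0.30/0.80 = 37.5th at 20%. The reported lower quartile is the (0.25 − s)/(1 − s) quantile: 0.20/0.95 = 21st at 5%, 0.05/0.80 = 6th at 20%. The lower quartile is the more exposed.

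**Reach of the LEN route.** Section 5 dates LEN approval to June 2025 and the study ends on 31 December 2025, so at most about 184-213 calendar days are affected, and only for users indexed from about mid-2024.

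**Reach of the oral exclusion.** It stops at 30 June 2025. An oral starter of 31 December 2024 is followed to 31 December 2025, so a CAB LA injection from 1 July 2025 does not exclude that person and the later days count as uncovered by oral PrEP. LEN use never excludes.

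**The case against.** The best defence is that nothing contradicts anything. The measure is openly coverage by one drug over a fixed window, the censoring list is the same wherever it appears, and such a proportion is a legitimate summary of adherence and persistence combined. Injection timing is assessed separately (Table 3), and Objective 3.4 reports switching and bridging. That stands as a reason to keep the figure. It does not explain the adherence label or show how much of the uncovered time was spent on other PrEP.

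Three stronger readings are tempting and not supported:

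- **All oral switchers are removed.** Only those injected with CAB LA by 30 June 2025 are. The others stay under the same rule as CAB LA users.
- **Protected Veterans are classed as non-adherent.** No adherence threshold or class is built on coverage.
- **The comparison is biased against CAB LA.** Switching lowers CAB LA coverage, and the exclusion may raise oral coverage. But CAB LA also receives a 7-day window credit per injection with no stated oral equivalent, which pushes the other way. The exclusion is also limited in size: even if all 748 CAB LA users had come from oral PrEP, they equal 748/15,477 = 4.8% of the oral count. No oral-versus-CAB LA test is planned.

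Replacing the measure with one censored at any other PrEP also has a cost. It would cut off oral bridging and give switchers near-full scores, while those who stop all PrEP keep their uncovered days.

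**Conclusion.** The point holds in a limited form. The coverage measure is drug-specific and uncensored at a change of PrEP, so it merges time on another PrEP with time on none under the name of adherence. This affects CAB LA users and, to a lesser extent, oral users indexed from about mid-2024. Because oral users who received CAB LA by 30 June 2025 are excluded on post-index information, the two percentages described together do not handle switching alike.

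The effect on one person follows from the protocol's own credits and the assumed schedule: 43% for an on-schedule user who switches at day 150. The cohort effect, about 3-11 points on the mean, rests on an assumed 5-20% switching at that day with everyone else fully covered. The reported median would move less than the lower quartile. The actual size and the net direction remain unknown.

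**What to change.** In Table 2, Section 7.3.3 (Adherence, a and b) and Section 7.7.1.1:

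1. Keep the existing figure, and label it drug-specific coverage combining adherence and persistence.
2. For both cohorts, add the proportion of days covered by any PrEP (oral, CAB LA or LEN), each day counted once, over the same 12 months. The gap between the two lines is time on another PrEP; what remains uncovered is time without recorded PrEP.
3. Optionally, add a sensitivity figure censored at the start of another modality, stating that oral bridging is not treated as a switch.
4. State that the oral and CAB LA figures are not directly comparable because of the oral-only exclusion, or also report oral coverage with those later switchers included.

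The cost is one or two extra output lines, built from PrEP records that Objective 3.4 already needs. The switch-censored figure is subject to informative censoring and should stay a sensitivity analysis.
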